Participants who sign the informed consent form and meet all the eligibility criteria will be enrolled in the study. [REDACTED]

[REDACTED]

Selection of Study Population

The clinical study can fulfill its objectives only if appropriate participants are enrolled.

The following criteria are designed to select participants for whom protocol requirements are considered appropriate.

Participants who meet all inclusion criteria and none of the exclusion criteria will be enrolled in the study and assigned a participant No./ID in sequential order (i.e., 01, 02, 03, etc.)

Inclusion Criteria

- Healthy candidates [REDACTED]
- Seeking treatment of cellulite in the thigh and/or buttock areas

- [REDACTED]

- █ [REDACTED]
- █ [REDACTED]
- █ [REDACTED]

- Participant must be able to provide written informed consent, understand and comply with all study-related procedures and follow-up visits.

Exclusion Criteria

- █ [REDACTED]
- █ [REDACTED]
- █ [REDACTED]
- █ [REDACTED]
- █ [REDACTED]
- █ [REDACTED]
- █ [REDACTED]
- █ [REDACTED]
- █ [REDACTED]
- █ [REDACTED]
- █ [REDACTED]

- Any other condition/disease/situation which, as deemed by the PI, would preclude participant from safely participating in or completing the study visits or that may confound study results.

[REDACTED]

[REDACTED]

[REDACTED]

PI's and participant's assessment of the thigh and/or buttock, but no fewer than 7 and no

[REDACTED]

[REDACTED]

[REDACTED]

[REDACTED]

[REDACTED]

[REDACTED]

[REDACTED]

[REDACTED]

[REDACTED]

[REDACTED]

[REDACTED]

[REDACTED]

[REDACTED]

[REDACTED]

[REDACTED]

[REDACTED]

[REDACTED]

UNSCHEDULED VISITS

An unscheduled visit may be performed at any time during the study at the participant's request or as deemed necessary by the study investigator. The date and reason for the visit will be recorded in the source document.

PARTICIPANT WITHDRAWAL AND EARLY TERMINATION

Participants may withdraw from the study at any time at their own request or withdrawn from at any time at the discretion of the Investigator for safety, behavioral, or administrative reasons. The Investigator should inquire about reason for withdrawal, request the participant to return for a final visit, and follow up with any unresolved adverse events. The Investigator should notify the Sponsor of any participants withdrawal or discontinuance.

[REDACTED]

[REDACTED]

[REDACTED]

[REDACTED]

[REDACTED]

- [REDACTED]

- [REDACTED]

- [REDACTED]

[REDACTED]

[REDACTED]

[REDACTED]

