3 STUDY DESIGN AND PROCEDURES

This is a non-significant risk, multi-center, multi-treatment (2 treatment sessions) prospective trial for safety, and effectiveness using ZELTIQ Aesthetics, Inc.'s RAP device for the improvement in the appearance of cellulite performed at up to four (4) clinical research sites in the United States.

Up to sixty (60) healthy participants between the age of 18-50 will be enrolled in this study.

Participants who sign the informed consent form and meet all the eligibility criteria will be enrolled in the study. Each participant will undergo acoustic rapid pulse (RAP) treatment sessions on both of their thighs and/or buttocks.

Total study duration is anticipated to be at or less than 60 weeks from the first participant visit to the last participant observation visit. A total of up to six (6) visits are planned for this study as shown in Table 1 of the protocol.

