5.5 BODY-Q™ APPRAISAL OF CELLULITE (ASSESSMENT 4 IN THE PROTOCOL)

This self-administered 11-item scale measures how much someone is bothered by the appearance of cellulite. At each assessment, the raw scores for the set of items in a scale are added together to produce a total raw score. If less than 5 questions are missing, the within person mean for the completed items will be imputed for the missing items prior to computing a total raw score. The total raw score cannot be imputed if 5 or more questions are missing. Total raw scores are then converted to a Rasch transformed score in the range of 0 (worst) to 100 (best) using the Conversion Table. Both total raw scores and Rasch transformed scores will be captured in the CRF. The raw scores are scored from 1 to 4, where higher scores indicate the patient is less bothered:

Extremely bothered = 1

Moderately bothered = 2

A little bothered = 3

Not at all bothered = 4

Sum Score	Equivalent Rasch Transformed Score (0-100)
11	0

12	11
13	16
14	20
15	23
16	25
17	28
18	30
19	32
20	34
21	36
22	38
23	40
24	42
25	44
26	46
27	47
28	49
29	51
30	53
31	55
32	58
33	60
34	62
35	65
36	68
37	71
38	74
39	77
40	80
41	83
42	87
43	93
44	100

5.6 BODY-Q™ SATISFACTION WITH HIPS & OUTER THIGHS AND SATISFACTION WITH BUTTOCKS (ASSESSMENT 4 IN THE PROTOCOL)

Hips & Outer Thighs is a self-administered 5-item scale measuring satisfaction with the appearance of the hips and outer thighs. Buttocks is a self-administered 5-item scale measuring satisfaction with the appearance of the buttocks. At each assessment, for both scales, the raw scores for the set of items in a scale are added together to produce a total raw score. If less than 3 questions are missing, the within person mean for the completed items will be imputed for the missing items prior to computing a total raw score. The total raw score cannot be imputed if 3 or more questions are missing. Total raw scores are then converted to a Rasch transformed score in the range of 0 (worst) to 100 (best) using the Conversion Table. Both total raw scores and Rasch transformed scores will be captured in the CRF. The raw scores are scored from 1 to 4, where higher scores indicate the patient is more satisfied:

Very Dissatisfied = 1

Somewhat Dissatisfied = 2

Somewhat Satisfied = 3

Very Satisfied = 4

Sum Score	Equivalent Rasch Transformed Score (0-100)
5	0
6	13
7	19
8	24
9	29
10	33
11	38
12	43
13	48
14	54
15	63
16	73
17	80
18	86
19	93
20	100

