7.1.3 Evaluable

The Evaluable population consists of participants in the Safety population who completed the Resonic treatment plan (completed two treatment sessions) bilaterally for at least one location.

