9.2.4 Exploratory Effectiveness Analyses

All exploratory effectiveness analyses will be descriptive and summarized using the Evaluable population.

- Number and proportion of participants who have one or two sides improved at the 4-week post-first treatment, 12, 26, and 52-week post-final treatment visits via the Participant Satisfaction Survey.
- Number and proportion of sides that are improved at the 4-week post-first treatment, 26, and 52-week post-final treatment visits via the Participant Satisfaction Survey.
- Descriptive statistics for overall average pain per participant at the two treatment visits.
- Descriptive statistics for GAIS score at the 4-week post-first treatment, 12, 26, and 52-week post-final treatment visits via the investigator GAIS.
- Descriptive statistics for actual and change from baseline in Body Q™ Appraisal of Cellulite, Satisfaction with Buttocks, and Satisfaction with Hip & Outer Thigh Rausch transformed total scores at the 4-week post-first treatment, 12, 26, and 52-week post-final treatment visits.

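### The BODY-Q buttocks and hip/outer-thigh satisfaction scores are summarised over all Evaluable participants, whichever location was treated, so the mean change may mix treated and untreated areas

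*SAP*

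**What the plan says.** **Treatment and eligibility.** SAP 3 describes "treatment sessions on both of their thighs and/or buttocks". The protocol's inclusion criteria use the same either-or-both wording: "Seeking treatment of cellulite in the thigh and/or buttock areas". Treatment at a single location is therefore allowed.

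**Population.** SAP 7.1.3 defines Evaluable as members of the Safety population "who completed the Resonic treatment plan (completed two treatment sessions) bilaterally for at least one location". One completed location is enough; the other may be untreated or only partly treated.

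**Scales.** SAP 5.6 describes two instruments, each tied to one body area: "Buttocks is a self-administered 5-item scale measuring satisfaction with the appearance of the buttocks", and "Hips & Outer Thighs is a self-administered 5-item scale measuring satisfaction with the appearance of the hips and outer thighs". It scores both at each assessment and sets no condition on which location was treated.

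**Analysis.** SAP 9.2.4 states: "All exploratory effectiveness analyses will be descriptive and summarized using the Evaluable population". The list that follows includes actual values and change from baseline for both scales, named there as "Satisfaction with Buttocks, and Satisfaction with Hip & Outer Thigh Rausch transformed total scores". Section 15.1 gives Evaluable as the population for Table 14.2.5.2 (buttocks) and Table 14.2.5.3 (hip and outer thigh), with no subset. Location is not among the subgroups in SAP 6.7, which in any case apply only to the primary endpoint.

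**The concern.** A location-specific scale is paired with a population that is not location-specific. A programmer following the SAP to the letter would put any available buttocks score from a thigh-only participant into the buttocks mean, and any available hip and outer thigh score from a buttock-only participant into the other mean. Someone who finished both thigh sessions but only one buttock session would also count in the buttocks table.

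The study has no concurrent control group (SAP 5.1 uses baseline photographs as the control) and no formal test (SAP 6.2). For these scales the descriptive change from baseline is the whole result. If the mean combines people treated at that location with people who were not, it does not estimate the change in satisfaction with a treated area. Readers could not undo the mixing, because neither table is split by location.

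**Working it through.** The documents state no expected change, location mix, power or threshold for these scales, so there is no figure of the plan's own to reproduce. The check has two parts: reading the sections together, and simple mixture arithmetic under stated assumptions.

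**1. Can a participant not fully treated at a location fall within that location's table?**
- SAP 3 permits treatment of thighs only, buttocks only, or both.
- SAP 7.1.3 makes a participant Evaluable after completion at one location.
- SAP 9.2.4 and Section 15.1 summarise both scales in Evaluable participants.
- SAP 5.6, 6, 6.7, 9.1.3, 9.2.4 and 15.1 add no location restriction.

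The stated rule therefore admits such a participant. Whether a score exists to be summarised depends on who is given which scale, and the visible text does not say.

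**2. Size, if the scores exist.** Let p be the share of Evaluable participants with scores who completed both sessions bilaterally at the location. Let dT be their mean change and dU the mean change in the rest.

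- Mean over all Evaluable = p × dT + (1 − p) × dU
- Dilution relative to the treated mean = (1 − p) × (dT − dU)

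The dilution is zero when p = 1 or when dU = dT. It is towards no change only if dT exceeds dU (with dT positive).

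For illustration, a raw score moving from 10 to 15 goes from 33 to 63 on the conversion table in SAP 5.6, so dT = 63 − 33 = 30. This movement, the values of dU and the values of p are all assumptions.

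| p | dU = 0 | dU = 5 | dU = 10 |
|---|---|---|---|
| 1.00 | 30.0 | 30.0 | 30.0 |
| 0.90 | 27.0 | 27.5 | 28.0 |
| 0.75 | 22.5 | 23.8 | 25.0 |
| 0.50 | 15.0 | 17.5 | 20.0 |
| 0.25 | 7.5 | 11.2 | 15.0 |

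Example: p = 0.50 and dU = 5 gives 0.50 × 30 + 0.50 × 5 = 17.5.

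**3. Spread.** With a common SD s within each group, the variance of change over all Evaluable = s² + p(1 − p)(dT − dU)². Taking s = 15 (assumed), p = 0.50, dT = 30 and dU = 0 gives 225 + 0.25 × 900 = 450, an SD of 21.2. The ratio of mean to SD falls from 30/15 = 2.0 to 15/21.2 = 0.71.

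**4. A bound from the Evaluable definition.** Every Evaluable participant has at least one completed location. If both scales are scored for everyone, the two shares therefore sum to at least 1. If p is 0.25 for one scale, it is at least 0.75 for the other. If nobody completed both locations, the two shares average 0.5.

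**The case against.** A reader might infer that participants untreated at a location are certainly in these means, and that both tables are therefore biased towards no change. The documents do not support that.

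- **Who completes each scale is not visible.** SAP 5.6 says how the scales are scored and points to Assessment 4 in the protocol, whose text cannot be seen in the public version. If each participant receives only the scale for the treated area, the other score is absent. SAP 5.6 allows no total score when three or more of the five items are missing, and SAP 6.3 rules out imputation. Each table would then hold only participants given that scale, and untreated areas would not enter. This stands, and it makes the point conditional. It would not by itself exclude participants partly treated at a location.
- **The purpose of the tables is not stated.** Nothing says they are meant to show satisfaction with the treated area. A summary over all Evaluable participants is coherent, though less informative. This also stands: the point concerns a better-targeted summary and does not rest on a contradiction between sections.
- **No change at untreated areas is an assumption.** Self-rated satisfaction with an untreated or neighbouring area may change for reasons other than the device. With a 10-point change there, the 50:50 example gives 20.0, compared with 15.0 under no change. The direction depends on treated areas changing more.
- **Little depends on it.** The endpoints are exploratory and descriptive, with no test or success threshold, and Listings 16.2.6.5.2 and 16.2.6.5.3 show scores by participant. This limits the severity but does not remove the ambiguity in the two summary tables.

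**Conclusion.** The point holds in conditional form. As written, the SAP summarises two location-specific scales in a population that needs completed treatment at only one location. If participants also complete the scale for a location where they were not fully treated, the mean change describes a mixture, and it is diluted if treated areas change more than the others.

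The amount cannot be computed from the documents. With the assumed 30-point treated change, it runs from nothing (everyone completed at both locations) to half (50% completed there, no change in the rest), and more at smaller shares. It is also nothing if each scale is administered only to participants who completed treatment at the matching location. The location mix, the 30 points, the change in the remaining participants and the SD are all assumptions.

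Severity is low. The primary endpoint, the secondary endpoint and the safety analyses do not use these scales. The Appraisal of Cellulite scale is not tied to one location and is not affected.

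**What to change.** In SAP 9.2.4 and in Tables 14.2.5.2 and 14.2.5.3, present each location scale for Evaluable participants who completed both sessions bilaterally at the matching location, with n. Show the remaining Evaluable participants with a score in a separate descriptive column. Keeping that column is better than moving those scores to the listings, because in an uncontrolled study this is the only group that could show background change in satisfaction. State in SAP 5.6 who completes each scale. If administration already follows the treated location, one sentence there settles the question for untreated areas.

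The cost is small. Completion by location must already be derived to define Evaluable, so no new data are needed, only one flag and one more column in each of two tables. The downside is a smaller n per column in a study of at most 60 participants.

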10 SAFETY EVALUATIONS

10.1 ADVERSE EVENTS AND ADVERSE DEVICE EFFECTS

An adverse event (AE) is defined as any unfavorable or unintended sign, symptom, or disease that occurs or is reported by the participant to have occurred, or worsening of a pre-existing condition. An AE may or may not be related to the study treatment.

An adverse device effect (ADE) is defined as an AE related to the use of an investigational medical device (Was the event caused by an Investigation Device? = Yes in the CRF).

AEs and ADEs will be coded using MedDRA version 26.0.

An overall summary will present the number and proportion of participants with AEs, serious adverse events (SAEs), ADEs, serious adverse device effects (SADEs), unanticipated AEs, and unanticipated ADEs using the Safety population.

In addition, the number and proportion of participants will be summarized by SOC and PT sorted in decreasing frequency. These summaries will be given by treatment in separate tables for each of the following event sets using the Safety population:

- AEs
- SAEs
- ADEs
- SADEs
- Unanticipated AEs
- Unanticipated ADEs

If a given participant experiences an AE that maps to the same PT/SOC more than once, the participant will be counted only once for the SOC/PT.

All AEs and ADEs will be presented in a by-participant listing.

The number and proportion of participants with known physiological responses (Red/pink hair follicles (folliculitis), Pain/Discomfort, Itchy Skin, Scaly Skin, Erythema, Edema, Purpura, Micro Blistering, Bruising/Contusion, Scabbing, Heat, Scratches, Crusting, Pinpoint Redness/Bleeding (petechiae), Sensation of Cold, Stinging, Tingling, Pinching, Hair removal, or Other) will be summarized for the Safety population based on Physiological Response Assessment collected on the Visit CRF form.

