- All AEs must be recorded in the participant’s medical records and in the case report form. AEs will be reported using customary medical terminology along with the following information: the onset and end dates, whether the event is considered to be a SAE, the impact the event had on study treatment, the

severity of the event, the causality of the event, whether treatment was given as a result of the event, and the outcome of the event.

2. Impact on Study Treatment

- The impact the event had on the study treatment will be assessed as either: none, study treatment interrupted, study treatment discontinued, or not applicable. The “not applicable” assessment will be used only when the participant is in the observation phase of the protocol.

3. Causality Assessment

- AEs will be assigned a relationship (causality) to the study treatment. The Investigator will be responsible for determining the relationship between an AE and the study treatment. The type of event, organ system affected, and timing of onset of the event will be factors in assessing the likelihood that an AE is related to the study treatment. Relationship of AEs to study treatment will be classified as follows:
 - i. Definitely related: This category applies to those AEs that the Investigator feels are incontrovertibly related to the study treatment. An AE may be assigned an attribution of definitely related if or when it meets all of the following criteria: (1) it follows a reasonable temporal sequence from administration of the study treatment; (2) it could not be reasonably explained by the known characteristics of the participant’s clinical state, environmental or toxic factors, or other modes of therapy administered to the participant; (3) it follows a known response pattern to treatment with the study treatment.
 - ii. Probably related: This category applies to those AEs which, after careful medical consideration at the time they are evaluated, are felt with a high degree of certainty to be related to the study treatment. An AE may be considered probable if or when (must have three): (1) it follows a reasonable temporal sequence from administration of the study treatment. (2) It could not readily have been produced by participant’s clinical state, environmental or toxic factors, or other therapies administered to the participant. (3) Disappears or is decreased upon discontinuation of the study treatment. (4) It follows a known response pattern to treatment with the study treatment.

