 - iii. Possibly related: This category applies to those AEs which, after careful medical consideration at the time they are evaluated, are judged unlikely but cannot be ruled out with certainty to the study treatment. An AE may be considered possible if or when (must have two): (1) it follows a reasonable temporal sequence from administration of the study treatment. (2) It could not readily have been produced by participant’s clinical state, environmental or toxic factors, or other therapies administered to the participant. (3) Disappears or is decreased upon discontinuation of the study treatment. (4) It follows a known response pattern to treatment with the study treatment.

- iv. Remotely related: In general, this category can be considered applicable to those AEs which, after careful medical consideration at the time they are evaluated, are judged likely to be unrelated to the study treatment. An AE may be considered unlikely if or when (must have two): (1) it does not follow a reasonable temporal sequence from administration of the study treatment. (2) It could not readily have been produced by participant's clinical state, environmental or toxic factors, or other therapies administered to the participant. (3) Disappears or is decreased upon discontinuation of the study treatment. (4) It does not follow a known response pattern to treatment with the study treatment.
- v. Unrelated: This category applies to those AEs which, after careful consideration at the time they are evaluated, are clearly and incontrovertibly due to extraneous causes (disease, environment, etc.) and determined with certainty to have no relationship to the study treatment.

4. Outcome Assessment

- The outcome of the event will be assessed as either: resolved, resolved with sequelae, ongoing, or death. Only one AE per participant is allowed to have an outcome assessment as "death." If there are multiple causes of death for a given participant, only the primary cause of death will have an outcome of death.

5. Serious Adverse Events

- A Serious Adverse Event (SAE) is defined as any AE that:
 - i. Results in death
 - ii. Is life threatening (the participant is at immediate risk of dying from the adverse experience)
 - iii. Requires participant hospitalization or prolongs existing hospitalization
 - iv. Results in persistent or significant disability/incapacity
 - v. Is a congenital anomaly/birth defect

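### No planned summary table reports adverse events or device effects by severity, outcome, duration or impact on treatment, although the protocol collects all four for every event

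*SAP*

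**What the plan says.** **Collection.** The protocol (Adverse Events, item 1) requires each AE to be entered in the case report form with "the onset and end dates, whether the event is considered to be a SAE, the impact the event had on study treatment", and then "severity of the event, the causality of the event, whether treatment was given as a result of the event, and the outcome of the event". Impact on treatment (item 2) is graded as "none, study treatment interrupted, study treatment discontinued, or not applicable". Outcome (item 4) is graded as "resolved, resolved with sequelae, ongoing, or death". Events are followed until they resolve or the participant finishes the study, and outcome is then assessed a final time.

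**Analysis.** SAP 10.1 states: "An overall summary will present the number and proportion of participants with AEs, serious adverse events (SAEs), ADEs", continuing with serious device effects, unanticipated AEs and unanticipated device effects. The same six event sets are then tabulated by SOC and PT in the Safety population. For repeated events, "the participant will be counted only once for the SOC/PT"; there is no rule for taking the worst severity or worst outcome. The table list in SAP 15.1 matches this text: 14.3.1.1 is the overall count and 14.3.1.2 to 14.3.1.7 are the six SOC/PT tables. Known physiological responses go into Table 14.3.2, again as participant counts.

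**Listings.** SAP 10.1 puts all AEs and device effects into by-participant listings, and SAP 15.2 says that listings carry all the data available.

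**The concern.** The secondary safety objective in SAP 2.2 covers the period after every session and every follow-up visit, and visits run to 52 weeks after the final treatment. That objective asks how bad the effects were and whether they went away. A table of participants who ever had an event answers neither question once seriousness is set aside.

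The device is used in healthy people seeking a cosmetic improvement. If serious events are few, which is an assumption because the visible documents give no expected rate, the safety conclusion will depend largely on the severity and persistence of non-serious local effects.

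The gap also works against the sponsor. A statement in the study report that effects were mild and transient could not be drawn from the pre-specified tables. It would have to be tallied from listings afterwards, under rules that nobody fixed in advance.

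**Working it through.** The documents state no safety rate, error rate or power for this point, so there is no planned figure to reproduce. The check compares what is collected with what is tabulated.

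| AE field (protocol, Adverse Events) | In Tables 14.3.1.1 to 14.3.1.7? |
|---|---|
| Serious or not | Yes, as separate event sets |
| Causality | Partly, through the yes/no device-effect split |
| Severity | No |
| Impact on study treatment | No |
| Treatment given for the event | No |
| Outcome | No |
| Onset and end dates | Not for duration or resolution; onset only if by treatment means by session |

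Unanticipated status is also tabulated.

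**What this does to a count.** Assume all 60 planned participants are treated, and take two participants with non-serious, anticipated, device-related events under the same PT.

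- Participant A has a mild event that resolves within days. Contribution to the AE row, the device-effect row and the PT row: 1/60 = 1.7% each.
- Participant B has a severe event still ongoing at week 52. Contribution to the same rows: 1/60 = 1.7% each.

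With N treated instead of 60, both contributions are 1/N, so they remain equal. They would differ only if B's event met a seriousness criterion or was unanticipated, because it would then also enter another table.

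**Resolution over time.** SAP 12 plans an informal interim once the last participant has reached week 12 after the second treatment, with an optional one at week 26. By then the Safety population is complete, so its denominator no longer changes. If the AE tables are run at these cuts and again at the end, each cumulative proportion can only stay level or rise, apart from data corrections, even if every event has resolved in between.

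**Physiological responses.** SAP 10.1 names many local effects here, including erythema, edema, purpura and bruising. Table 14.3.2 is not specified by visit, so it cannot show persistence either. The responses are recorded on the Visit form, and the protocol has them assessed at treatment and follow-up visits, so a by-visit display is possible.

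**Availability.** SAP 14 drops several assessments for lack of data. None of the AE fields above is among them.

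**The case against.** The strongest reply is that nothing is lost. The listings would show severity, dates, outcome and treatment impact for every event. In a single-arm descriptive study of up to 60 people, a reader could find each unresolved device effect there. This stands as far as it goes, and a reader who infers that the plan discards these data would be wrong. But a listing gives no count or proportion, and no rule for the worst of several events.

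Other stronger readings are tempting and also fail:

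- **That the tables record only occurrence.** They separate seriousness, device relationship and unanticipated status. The protocol's seriousness criteria include persistent or significant disability, so some severe lasting effects would reach the serious-event tables.
- **That a brief bruise counts the same as a lasting severe effect.** Bruising is a named physiological response with its own table, and the protocol mentions such responses separately from AEs. The visible text does not stop a bruise being recorded as an AE, but the argument should not rest on it.
- **That stops caused by AEs are invisible.** SAP 7.2 reports reasons for withdrawal and SAP 8 reports how many completed one or both treatments. Participants who stop after one session stay in the Safety population. What is missing is a direct count of AEs that interrupted or discontinued treatment, including in people who stop treatment but remain in follow-up; such people can drop out of the Evaluable population.
- **That dates are wholly unused.** SAP 10.1 gives its SOC/PT summaries by treatment, which is undefined in a one-arm, two-session study. If it means by session, onset timing would be needed.
- **That no severity scale exists.** Much of the protocol is redacted, so its absence from the visible text is no ground for criticism.

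**Conclusion.** The point holds as a reporting gap. Of the fields collected for every AE, severity, outcome, duration and impact on treatment appear in none of the seven AE tables; nor does treatment given. Beyond the three splits that are tabulated, mild transient and severe ongoing events under one PT are indistinguishable, and resolution of device effects cannot be read from any planned summary.

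The size is limited. No endpoint, analysis population or success criterion is affected, and the information survives in the listings. The documents do not indicate how many such events to expect, so the 1/60 illustration shows equal counting, not likely frequency. The conclusion assumes that the tables will be built as SAP 10.1 and 15.1 describe them. The change is worth making because the study has a stated safety objective over follow-up and already collects what is needed to answer it.

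**What to change.** Keep the Safety population throughout.

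- **Table 14.3.1.1.** Add the number and proportion of participants: with AEs and with device effects by maximum recorded severity; with an AE whose impact was treatment interrupted or discontinued; with an AE that needed treatment; and with a device effect whose outcome is resolved with sequelae, or ongoing at last contact.
- **Table 14.3.1.4.** Show each device-effect PT by maximum severity, with the number ongoing at last contact. Give duration for resolved events only and label it so, or treat ongoing events as censored at last contact. A single median from onset and end dates would leave out ongoing events, which have no end date, and would understate duration.
- **Table 14.3.2.** Present known physiological responses by visit, because many local effects are recorded there.

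In the same edit, state what by treatment means in SAP 10.1.

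The cost is a little more programming and longer tables, using fields already on the case report form. Nothing changes in study conduct, sample size or data collection.
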